2.6 Rationale for Amendment #5 (addition of dose level 4)

[figure not shown]
Pevoneditstat, a first in class inhibitor of NEDD8 activating enzyme (NAE), prevents the activation of Cullin-RING ligases (CRL) necessary for proteasome mediated degradation of key regulatory proteins important in cell survival. In adults with solid tumors, the maximum tolerated dose (MTD) in combination with chemotherapy is 20-25 mg/m².^{28,29}

As a single agent in adults with MDS/AML the MTD for pevoneditstat infusions on days 1, 3, and 5 per cycle was determined to be 59 mg/m² and for melanoma or advanced solid tumors, was determined to be 67 mg/m². The recommended phase 2 dose for pevoneditstat monotherapy for that schedule is 50mg/m².^{1,30} In adults, the predominant dose limiting toxicity (DLT) was hepatotoxicity.

In our current Phase 1 Study of Pevoneditstat (MLN4924) a NEDD8 Activating Enzyme Inhibitor, in Combination with Temozolomide (TMZ) and Irinotecan (IRN) in Pediatric Patients with Recurrent or Refractory Solid Tumors (ADVL1615), 18 patients have enrolled and all were eligible and evaluable for cycle 1 dose limiting toxicity (DLT) assessment. Six patients each enrolled on pevoneditstat dose levels 1 (15mg/m²), 2 (20mg/m²), and 3 (25mg/m²). No pediatric patients experienced a DLT, and only 1 patient each experienced grade 3 elevated AST and elevated ALT, which resolved and did not meet criteria for dose-reduction.³³

The pharmacokinetics (PK) of pevoneditstat were similar in adult and pediatric studies. In our pediatric study, the mean area under the curve (AUC) at the 25 mg/m² dose level on day 8 (in combination with irinotecan and temozolomide) was 1296 hr•ng/mL, half-life (T $\frac{1}{2}$) was 5-6 hours, time to maximum concentration (Tmax) was 1 hour, and average clearance was 20 L/hr/m², comparable with adult trials (Figure 1).³¹ Both AUC and maximum concentration (Cmax) increased with dose level, but unlike the adult data, the increase appeared to be greater than dose-proportional. This was reflected in the Day 1 clearance which showed a small decrease with dose suggesting non-linear clearance.

Given that the recommended Phase 2 dose of pevoneditstat as a monotherapy for the current schedule is 50 mg/m² and the observed good tolerability of the combination of pevoneditstat, irinotecan and temozolomide in pediatric patients at 25 mg/m², we propose amending our trial to include a dose level 4 of 35 mg/m². Based on our pediatric PK data, we expect this dose level will result in a 40% increase in AUC and Cmax, equivalent to approximately an adult dose of 45 mg/m². If dose level 4 proves intolerable, we propose opening an expanded PK cohort at the 25 mg/m² dose (dose level 3).

3.0 SCREENING AND STUDY ENROLLMENT PROCEDURES

Patient enrollment for this study will be facilitated using the Slot-Reservation System in conjunction with the Oncology Patient Enrollment Network (OPEN), a web-based registration system available on a 24/7 basis. It is integrated with the NCI Cancer Trials Support Unit (CTSU) Enterprise System for regulatory and roster data and, upon enrollment, initializes the patient position in the RAVE database.

Access requirements for OPEN:

Investigators and site staff will need to be registered with CTEP and have a valid and active Cancer Therapy Evaluation Program-Identity and Access Management (CTEP-IAM) account (check at <<https://ctepcore.nci.nih.gov/iam/index.jsp>>). This is the same account (user id and password) used for credentialing in the CTSU members' web site. To perform registrations in OPEN, the site user must have been assigned the 'Registrar' role on the relevant Group or CTSU roster. OPEN can be accessed at <https://open.ctsu.org> or from the OPEN tab on the CTSU members' side of the website at <https://www.ctsu.org>.

3.1 Current Study Status

Investigators should refer to the COG website to determine if the study is currently open for accrual. If the study is listed as active, investigators should then access the Studies Requiring Reservations page to ensure that a reservation for the study is available. To

access the Studies Requiring Reservations page:

1. Log in to <https://open.ctsu.org/open/>
2. Click the **Slot Reservation** Tab. *The Site Patient page opens.*
3. Click the **Report** Tab. *The Slot Reservation Report opens. Available Slots are detailed per study strata.*

3.2 IRB Approval

NCI Pediatric CIRB approval or local IRB approval of this study must be obtained by a site prior to enrolling patients. Sites must submit CIRB/IRB approvals to the NCI's Cancer Trials Support Unit (CTSU) Regulatory Office and allow 3 business days for processing. The CTSU IRB Certification Form may be submitted in lieu of the signed IRB approval letter. All CTSU forms can be located on the CTSU web page (www.ctsu.org). Any other regulatory documents needed for access to the study enrollment screens will be listed for the study on the CTSU Member's Website under the Regulatory Tab.

Sites participating on the NCI CIRB initiative and accepting CIRB approval for the study are not required to submit separate IRB approval documentation to the CTSU Regulatory Office for initial, continuing or amendment review. This information will be provided to the CTSU Regulatory Office from the CIRB at the time the site's Signatory Institution accepts the CIRB approval. The Signatory site may be contacted by the CTSU Regulatory Office or asked to complete information verifying the participating institutions on the study.

Submitting Regulatory Documents:

Submit required forms and documents to the CTSU Regulatory Office via the Regulatory Submission Portal, where they will be entered and tracked in the CTSU RSS.

Regulatory Submission Portal: www.ctsu.org (members' area) → Regulatory Tab
→ Regulatory Submission

When applicable, original documents should be mailed to:

CTSU Regulatory Office
[name]
[name]

Institutions with patients waiting that are unable to use the Portal should alert the CTSU Regulatory Office immediately at [name] in order to receive further instruction and support.

For general (non-regulatory) questions, call the CTSU General Helpdesk at [name] or contact CTSU by email at [contact].

Study centers can check the status of their registration packets by accessing the Site Registration Status page on the CTSU Member's Website under the Regulatory Tab. (Note: Sites will not receive formal notification of regulatory approval from the CTSU Regulatory Office.)

3.3 Patient Registration

Prior to enrollment on study, patients must be assigned a COG patient ID number. This number is obtained via the COG Registry in the OPEN system once authorization for the release of protected health information (PHI) has been obtained.

3.4 Reservation and Contact Requirements

Before enrolling a patient on study, a reservation must be made through the OPEN website and the Study Chair or Vice Chair should be notified. (The patient will need a COG patient ID number in order to obtain a reservation). Patients must be enrolled within 7 calendar days of making a reservation.

Reservations may be obtained 24-hours a day through the OPEN website.

3.5 **Informed Consent/Accent**

The investigational nature and objectives of the trial, the procedures and treatments involved and their attendant risks and discomforts, and potential alternative therapies will be carefully explained to the patient or the patient's parents or guardian if the patient is a child, and a signed informed consent and assent will be obtained according to institutional guidelines.

3.6 **Screening Procedures**

Diagnostic or laboratory studies performed exclusively to determine eligibility for this trial must only be done after obtaining written informed consent. This can be accomplished through one of the following mechanisms: a) the COG screening protocol, b) an IRB-approved institutional screening protocol or c) the study-specific protocol. Documentation of the informed consent for screening will be maintained in the patient's research chart. Studies or procedures that were performed for clinical indications (not exclusively to determine eligibility) may be used for baseline values even if the studies were done before informed consent was obtained.

3.7 **Eligibility Checklist**

Before the patient can be enrolled, the responsible institutional investigator must sign and date the completed eligibility checklist. A signed copy of the checklist will be uploaded into RAVE immediately following enrollment.

3.8 **Institutional Pathology Report**

Immediately following enrollment, the institutional pathology report for the diagnosis under which the patient is being enrolled must be uploaded into RAVE. The report must include the associated study number and COG patient registration and accession numbers. Personal identifiers, including the patient's name and initials must be removed from the institutional pathology report prior to submission.

3.9 **Study Enrollment**

Patients may be enrolled on the study once all eligibility requirements for the study have been met. Patients who give informed consent for the protocol in order to undergo screening for eligibility are not considered enrolled and should not be enrolled until the screening is completed and they are determined to meet all eligibility criteria. Study enrollment is accomplished by going to the CTSU OPEN (Oncology Patient Enrollment Network) <https://open.ctsu.org/open/>. For questions, please contact the COG Study Research Coordinator, or the CTSU OPEN helpdesk at <https://www.ctsu.org/CTSUContact.aspx>. Patients must be enrolled before treatment begins. The date protocol therapy is projected to start must be no later than five (5) calendar days after the date of study enrollment. **Patients must not receive any protocol therapy prior to enrollment.**

3.10 **Dose Assignment**

The dose level will be assigned via OPEN at the time of study enrollment.

4.0 PATIENT ELIGIBILITY

All clinical and laboratory studies to determine eligibility must be performed within 7 days prior to enrollment unless otherwise indicated. Laboratory values used to assess eligibility must be no older than seven (7) days at the start of therapy. Laboratory tests need **not** be repeated if therapy starts **within** seven (7) days of obtaining labs to assess eligibility. If a post-enrollment lab value is outside the limits of eligibility, or laboratory values are older than 7 days, then the following laboratory evaluations must be re-checked within 48 hours prior to initiating therapy: CBC with differential, bilirubin, ALT (SGPT), and serum creatinine. If the recheck is outside the limits of eligibility, the patient may not receive protocol therapy and will be considered off protocol therapy. Imaging studies must be obtained within 14 days prior to start of protocol therapy (repeat the tumor imaging if necessary).

Clarification in timing when counting days: As an example, please note that if the patient's last day of prior therapy is September 1st, and the protocol requires waiting at least 7 days for that type of prior therapy, then that patient cannot be enrolled until September 8th.

Important note: The eligibility criteria listed below are interpreted literally and cannot be waived (per COG policy posted 5/11/01). All clinical and laboratory data required for determining eligibility of a patient enrolled on this trial must be available in the patient's medical or research record which will serve as the source document for verification at the time of audit.

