4.1.7 Organ Function Requirements

4.1.7.1 Adequate Bone Marrow Function defined as:

- a. For patients with solid tumors without known bone marrow involvement:
 - Peripheral absolute neutrophil count (ANC) $\geq 1000/\text{mm}^3$
 - Platelet count $\geq 100,000/\text{mm}^3$ (transfusion independent, defined as not receiving platelet transfusions for at least 7 days prior to enrollment).
 - Hemoglobin $\geq 8 \text{ g/dL}$
- b. Patients with known bone marrow metastatic disease will be eligible for study provided they meet the blood counts in [Section 4.1.7.1.a](#) (may receive transfusions provided they are not known to be refractory to red cell or platelet transfusions). These patients will not be evaluable for hematologic toxicity. At least 5 of every cohort of 6 patients on Part A1 must be evaluable for hematologic toxicity for the dose-escalation part of the study. If dose-limiting hematologic toxicity is observed, all subsequent patients enrolled must be evaluable for hematologic toxicity.

4.1.7.2 Adequate Renal Function defined as:

- Creatinine clearance or radioisotope GFR $\geq 70 \text{ mL/min}/1.73 \text{ m}^2$ or
- A serum creatinine based on age/gender as follows:

Age	Maximum Serum Creatinine (mg/dL)	
	Male	Female
6 months to < 1 year	0.5	0.5
1 to < 2 years	0.6	0.6
2 to < 6 years	0.8	0.8
6 to < 10 years	1	1
10 to < 13 years	1.2	1.2
13 to < 16 years	1.5	1.4
≥ 16 years	1.7	1.4

The threshold creatinine values in this Table were derived from the Schwartz formula for estimating GFR (Schwartz et al. J. Peds, 106:522, 1985) utilizing child length and stature data published by the CDC.

4.1.7.3 Adequate Liver Function defined as:

- Bilirubin (sum of conjugated + unconjugated) \leq upper limit of normal (ULN) for age
- SGPT (ALT) \leq 135 U/L. For the purpose of this study, the ULN for SGPT is 45 U/L.
- SGOT (AST) \leq 150 U/L. For the purpose of this study, the ULN for SGOT is 50 U/L.
- Serum albumin \geq 2.7 g/dL

4.1.7.4 Adequate Cardiac Function defined as:

- Shortening fraction of \geq 27% by echocardiogram, or
- Ejection fraction of \geq 50% by gated radionuclide study.
- No supraventricular arrhythmia on EKG
- Prolonged rate corrected QT (QTc) interval $<$ 500 msec

4.1.7.5 Adequate Pulmonary Function defined as:

- Pulse oximetry $>$ 94% on room air if there is clinical indication for determination (e.g. dyspnea at rest).

4.1.7.6 Adequate Neurologic Function defined as:

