6.2 Dose Modifications for Non-Hematological Toxicity (for patients \geq 12 months)

6.2.1 Patients who have any dose-limiting non-hematological toxicity (as defined in [Section 5.6.1](#)) may continue on protocol therapy upon meeting eligibility lab requirements or baseline but should receive subsequent doses of pevonédistat at the next lower dose level. Irinotecan and temozolomide should be continued at the same dose.

6.2.2 If the same non-hematological dose-limiting toxicity recurs after one dose reduction, the patient must be removed from protocol therapy.

6.2.3 Patients who have a dose-limiting non-hematological toxicity that does not resolve to baseline or eligibility within 21 days after the planned start of the next treatment cycle must be removed from protocol therapy.

6.2.4 Pevonédistat dose modification for hepatic toxicity:

In all cycles, AST, ALT, and bilirubin should be checked prior to each dose of pevonédistat and then once weekly for the remaining weeks of the study. It is anticipated that LFTs (AST, ALT, and occasionally bilirubin) may be elevated for approximately 48 hours following the end of the 1st pevonédistat infusion. See [Appendix III](#) for toxicity grading table.

For Grade 2 or 3 AST, ALT, or bilirubin on or after Cycle 1 Day 8, pevonédistat should be held. Once the elevated AST, ALT, or bilirubin returns to \leq Grade 1 by the end of the current cycle, then pevonédistat dose may be resumed at the same dose. If a dose is delayed due to increased LFTs, pevonédistat needs to be administered by Day 25 of Cycle 1 or Day 18 of subsequent cycles (within a cycle there should be a maximum of 13 days between doses).

For Grade 4 AST, ALT, or bilirubin on or after Cycle 1 Day 8, the pevonédistat dose should be held for the remainder of the cycle. If the elevated AST, ALT, or bilirubin return to \leq Grade 1, then pevonédistat may be restarted at the next cycle at the next lower dose level.

Interventions for Dose Modifications Secondary to Elevated AST, ALT, or bilirubin	
Grade 2	Hold pevonédistat until resolved to \leq Grade 1
Grade 3	Hold pevonédistat until resolved to \leq Grade 1
Grade 4	Hold pevonédistat for remainder of cycle. For subsequent cycle resume at next lower dose level if resolved to \leq Grade 1

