8.0 EVALUATIONS/MATERIAL AND DATA TO BE ACCESSIONED

8.1 Required Clinical, Laboratory and Disease Evaluation

All clinical and laboratory studies to determine eligibility must be performed within 7 days prior to enrollment unless otherwise indicated. Laboratory values used to assess eligibility (see [Section 4.0](#)) must be no older than seven (7) days at the start of therapy. Laboratory tests need **not** be repeated if therapy starts **within** seven (7) days of obtaining labs to assess eligibility. If a post-enrollment lab value is outside the limits of eligibility, or laboratory values are older than 7 days, then the following laboratory evaluations must be re-checked within 48 hours prior to initiating therapy: CBC with differential, bilirubin, ALT (SGPT) and serum creatinine. If the recheck is outside the limits of eligibility, the patient may not receive protocol therapy and will be considered off protocol therapy. Imaging studies must be obtained within fourteen (14) days prior to start of protocol therapy (repeat the tumor imaging if necessary). See [Appendix XIII](#) for Therapy Delivery Maps for Cycle 1 and all subsequent cycles.

Studies to be Obtained	For all patients		For patients \geq 12 months ONLY	For patients $<$ 12 months ONLY
	Pre-Study	During Cycle 1	Prior to Subsequent Cycles [^]	Prior to Subsequent Cycles [^]
History	X	X	X	X
Physical exam with vital signs ⁷	X	Weekly	X	X
Height, weight, BSA	X		X	X
Performance status	X		X	X
CBC, differential, platelets	X	Twice weekly ¹	Weekly ^{1,2,3}	Weekly ^{1,2,3}
Electrolytes including Ca ⁺⁺ , PO ₄ , Mg ⁺⁺	X	Weekly	X	Weekly
Creatinine	X	Weekly	X	Weekly
ALT, AST, bilirubin	X	Prior to each dose of pevoneditat, then weekly*	Prior to each dose of pevoneditat, then weekly*	Prior to each dose of pevoneditat, then weekly*
ECHO/EKG	X			
Albumin	X		X	X
Pulse Oximetry	X		X	X
Pregnancy test ⁴	X		X	X
Tumor disease evaluation	X	End of Cycle 1	End of Cycle 2 then every other cycle x 2 then q 3 cycles ⁵	End of Cycle 2 then every other cycle x 2 then q 3 cycles ⁵
Bone Marrow Evaluation ⁸	X	End of Cycle 1	End of Cycle 2 then every other cycle x 2 then q 3 cycles ⁵	End of Cycle 2 then every other cycle x 2 then q 3 cycles ⁵
Pharmacokinetics ⁶ (required)	X	X		
Pharmacodynamics (optional)	X	X		
INR	X			

[^] Studies may be obtained within 72 hours prior to the start of the subsequent cycle.

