10.0 CRITERIA FOR REMOVAL FROM PROTOCOL THERAPY AND OFF STUDY CRITERIA

10.1 Criteria for Removal from Protocol Therapy

- a) Clinical (including physical examination or serum tumor markers) or radiographic evidence of progressive disease (See [Section 12.0](#))
- b) Adverse Events requiring removal from protocol therapy (See [Section 6.0](#))
- c) Refusal of protocol therapy by patient/parent/guardian
- d) Non-compliance that in the opinion of the investigator does not allow for ongoing participation.
- e) Completion of 17 cycles of therapy.
- f) Physician determines it is not in the patient's best interest.
- g) Repeated eligibility laboratory studies (CBC with differential, bilirubin, ALT (SGPT) or serum creatinine) are outside the parameters required for eligibility prior to the start of pevonedistat (See [Section 8.1](#)).
- h) Study is terminated by Sponsor.
- i) Pregnancy

Patients who are removed from protocol therapy during Cycle 1 should continue to have the required observations in [Section 8.1](#) until the originally planned end of the cycle or until all adverse events have resolved per [Section 13.4.4](#), whichever happens LATER. The only exception is with documentation of the patient's withdrawal of consent. Patients who are removed from protocol therapy in subsequent cycles should have the necessary observations to ensure adequate clinical care.

Patients who are off protocol therapy are to be followed until they meet the criteria for Off Study (see below). Ongoing adverse events, or adverse events that emerge after the patient is removed from protocol therapy, but within 30 days of the last dose of investigational agent, must be followed and reported via RAVE and CTEP-AERS (if applicable). Follow-up data will be required unless consent is withdrawn.

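### AST is an entry limit but is missing from the pre-treatment recheck and removal lists, so a raised AST does not clearly bar the first pevonedistat dose

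*Combined protocol and SAP*

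**What the plan says.** Section 4.1.7.3 sets the liver criteria for entry: bilirubin at or below the ULN for age, ALT at most 135 U/L, AST at most 150 U/L, and albumin at least 2.7 g/dL. It fixes the study reference values: "For the purpose of this study, the ULN for SGPT is 45 U/L" and "For the purpose of this study, the ULN for SGOT is 50 U/L".

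Section 4.0 calls for a recheck if a post-enrollment value falls outside the eligibility limits, or if the laboratory values are more than 7 days old. The tests to repeat are "CBC with differential, bilirubin, ALT (SGPT), and serum creatinine". The consequence follows: "If the recheck is outside the limits of eligibility, the patient may not receive protocol therapy". Section 8.1 repeats the instruction, again naming the tests to be done "within 48 hours prior to initiating therapy: CBC with differential, bilirubin, ALT (SGPT) and serum creatinine". Criterion 10.1(g) takes a patient off protocol therapy on the same set: "Repeated eligibility laboratory studies (CBC with differential, bilirubin, ALT (SGPT) or serum creatinine". AST is in none of the three.

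AST is nevertheless measured before the first dose. Section 6.2.4, the schedule in Section 8.1 and the Cycle 1 therapy delivery map (Appendix XIII-A, item h on Day 1) all require ALT, AST and bilirubin before each pevonedistat infusion.

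The hold rule in the text of Section 6.2.4 opens with "For Grade 2 or 3 AST, ALT, or bilirubin on or after Cycle 1 Day 8", and the Grade 4 rule starts on the same day. The table beneath it, titled "Interventions for Dose Modifications Secondary to Elevated AST, ALT, or bilirubin", prescribes holds by grade and states no start day.

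**The concern.** The plan measures AST before Day 1 and has an AST limit for entry, but the rule that stops treatment on a failed recheck leaves AST out. Read literally, a patient whose AST has risen above 150 U/L since enrollment is retested on four other items and may be dosed if those are acceptable.

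Section 2.6 names hepatotoxicity as the predominant adult DLT, and Section 2.3.1 lists elevated AST among the DLTs on the adult Day 1, 3, 5 schedule without dexamethasone. A patient who starts with raised AST is exposed to a known hepatotoxin at a value that would require a hold one week later.

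There is also a smaller cost to the data. If AST has not recovered by Day 8, pevonedistat must be held. Section 11.2.1 requires all prescribed pevonedistat doses for DLT evaluability, so an unresolved hold could cost an evaluable patient. A pre-existing elevation could also blur the attribution of a hepatic DLT in a cohort of at most six, where two DLTs stop escalation (Section 11.3).

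**Working it through.** No sample size, power or error rate depends on this point. The check compares the rules for ALT and AST, then follows a raised AST through them.

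**1. The two enzymes side by side** (Section 4.1.7.3, Appendix III, Sections 4.0, 6.2.4, 8.1 and 10.1)

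| | ALT | AST |
|---|---|---|
| Study ULN (U/L) | 45 | 50 |
| Entry limit ÷ ULN | 135 / 45 = 3.0 | 150 / 50 = 3.0 |
| Top of Grade 2 ÷ ULN | 225 / 45 = 5.0 | 250 / 50 = 5.0 |
| Top of Grade 3 ÷ ULN | 900 / 45 = 20.0 | 1000 / 50 = 20.0 |
| Drawn before the Day 1 dose | yes | yes |
| Hold at Grade 2 or above from Day 8 | yes | yes |
| On the recheck lists (4.0, 8.1) | yes | **no** |
| In criterion 10.1(g) | yes | **no** |

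In relative terms the plan gives the two enzymes the same limits, grades, monitoring and holds. They part only in the recheck and removal lists.

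**2. What a failing AST means.** The entry limit of 150 U/L is also the top of Grade 1. Any AST above it is therefore at least Grade 2 (151 to 250 U/L), and Appendix III grades it regardless of baseline.

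**3. Following the rules before Day 1.** Suppose AST is 151 U/L or more after enrollment, with CBC, bilirubin, ALT and creatinine within limits.

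- Section 4.0: the AST is out of limits, so a recheck is triggered. The required recheck does not include AST. The four listed tests pass, and nothing in the recheck rule bars therapy.
- Section 10.1(g): AST is not listed, so the criterion is not met.
- Section 6.2.4, text: the hold begins at Cycle 1 Day 8, so it does not apply.
- Section 6.2.4, table: no start day is given, so a site could read it as a hold on Day 1.
- Section 5.3: the return to the eligibility laboratory limits governs later cycles, not Day 1.

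Suppose instead that ALT is above 135 U/L, the same 3.0 × ULN. It is rechecked, and if it is still above the limit the patient does not start.

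**4. The age of the qualifying AST.** Eligibility tests may be 7 days old at enrollment (Section 4.0), and therapy may be projected to start up to 5 days later (Section 3.9): 7 + 5 = 12 days. Section 4.0 says eligibility values must be no more than 7 days old when therapy starts, but its remedy for older values again names only the four tests.

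**5. Exposure at stake.** Cycle 1 has four pevonedistat doses (Days 1, 8, 10 and 12). Only the first falls before the Day 8 hold rule: 1 of 4, single-agent, at most 35 mg/m² (Dose Level 4).

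**The case against.** The strongest objection is that a written rule already reaches Day 1. The table in Section 6.2.4 names AST, prescribes a hold at Grade 2 or above and carries no start day. On that view the defect is a mismatch between text and table, and the smaller edit would be to say that the hold covers Day 1. The mismatch is real, but the text of the same section starts at Day 8 for every grade, so the table alone cannot be relied on to stop the dose.

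Several limits on the importance of the point stand:

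- AST must qualify at enrollment, and the 7-day and 5-day windows are short. AST has to rise alone within days.
- Nothing forbids a site from repeating AST, and criterion 10.1(f) lets the physician stop treatment. Both are discretionary.
- Day 1 is single-agent at no more than 35 mg/m², against an adult monotherapy recommended dose of 50 mg/m² on Days 1, 3 and 5. Section 2.6 reports no DLT in 18 children at 15 to 25 mg/m², with one Grade 3 AST and one Grade 3 ALT elevation, which resolved. This lowers the stakes but says nothing about patients who start with raised AST.
- Barring the patient is harsher than the reversible hold used from Day 8, in a population without curative options. The plan already accepts that consequence for ALT and bilirubin.

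A short list used identically in three places might be deliberate. Section 6.2.4 expects liver tests to rise for about 48 hours after the first infusion, which may explain starting holds at Day 8. It gives no reason to give that first infusion when AST is already above the entry limit.

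**Conclusion.** The concern holds and is minor. AST is the only transaminase limit that the recheck and removal rules do not enforce, and Section 6.2.4 is inconsistent for the first dose. Per affected patient the direct exposure is one single-agent dose of at most 35 mg/m². The frequency of an isolated AST rise between enrollment and Day 1 cannot be estimated from the documents. No sample size or escalation rule changes.

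The conclusion assumes that sites apply the recheck lists as written and do not, on their own judgement, stop for a test that is not listed.

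**What to change.** Add AST (SGOT) to the recheck lists in Sections 4.0 and 8.1 and to criterion 10.1(g). An AST still above 150 U/L on the 48-hour recheck then bars the first dose, as ALT and bilirubin already do on recheck. Day 1 no longer depends on whether a site follows the text or the table of Section 6.2.4. The mismatch itself would remain, and stating a start day in the table would remove it.

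Albumin and INR are also entry criteria missing from the lists. They can stay off: unlike AST, they are not scheduled before each dose and have no hold rule. That reason does not explain the existing list, since creatinine is only weekly in Cycle 1. The case for AST rests on its parity with ALT.

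The cost is one term in three places. No extra draw is needed, because AST is already measured before Day 1 and the recheck sample is already being taken. The downside is that an occasional enrolled patient will not start therapy.
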